Rainbow Light	Active Health Teen Multi	3 tablets	200	100.00		
	Active Senior Multivitamin	1 tablet	200	400.00		
	Advanced Nutritional System	6 tablets	240	400.00		
	Complete Menopause Support	4 tablets	1000	400.00		
	Everyday Calcium with Enzymes	4 tablets	1200	200.00		
	Just Once Iron Free Safe Guard multivitamin	1 tablet	30	400.00		
	Just Once Food Based Calcium	1 tablet	500	200.00		
	Mens One Multivitamin	1 tablet	50	400.00		
	Nutritional Systems NutriStars	2 tablets	40	50.00		
	Prenatal One Multivitamin	1 tablet	200	400.00		
	Womens Nutritional System	6 tablets	1000	400.00		
	Womens One Multivitamin	1 tablet	200	400.00		
	Womens Whole Nutrition Liquid Multi	2 softgels	100	400.00		
	Mens Whole Nutrition Liquid Multi	2 softgels	100	400.00		
Reliv	RelivClassic	2 scoops	1000	400.00		
	RelivNow for kids	2 scoops	1000	400.00		
	Simplicity	1 scoop	500	200.00		
Rexall-Sundown	Complete Daily with Lutein	1 tablet	162	400.00		
	SunVite	1 tablet	162	400.00		
	Daily Multi Caplets	1 caplet	162	400.00		
	Complete Energy	1 caplet	100	400.00		

	Vitamins to Go Maximum	1 tablet	777	525.00		
	Daily Multi 50+	1 tablet	162	400.00		
	Osteo Bi-Flex Plus Calcium With Vitamins C and D	3 caplets	500	400.00		
Rite Aid	Whole Source Mature Adult Multivitamin/Mineral	1 tablet	165	400.00		
	Calcium Soft Chews	1 softchew	500	100.00		
	600mg Calcium Plus Vitamin D	1 tablet	600	200.00		
	Central Vite	1 tablet	162	30.00		
River's Edge	VitaPhil	1 tablet	100	400.00		RX only
Rugby	Advance Formula Cerovite	1 tablet	162	400.00		
	Cerovite Jr. Chewables	1 tablet	108	400.00		
	VITa-PMS	1 tablet	21	17.00		
	Calcium 600-D	1 tablet	600	200.00		
	Oysco 500 + D	1 tablet	500	200.00		
	Oysco D	1 tablet	400	125.00		
	Prenavite	1 tablet	200	400.00		
Schiff	Childrens chewables	1 chewtab	20	200.00		
	Guided Minerals Multi Minerals Complex	3 tablets	1200	400.00		
	Hair, Skin and Nails with MSM	2 tablets	170	800.00		
	Prime Years Multi Vitamin	1 softgel	100	400.00		
	Prostrate Health	2 capsules	29	400.00		
	Single Day Antioxidant Rich	1 tablet	10	400.00		
	Super Calcium 1200 with Vitamin D	2 softgels	1200	400.00		
	Sustained Release Single Day Multi Vitamin	1 tablet	25	400.00		
	Vegetarian Multiple with Beta Carotene	2 capsules	200	400.00		
Shaklee	Vita-Lea Iron Formula High Potency Multivitamin & Mineral	2 tablets	450	200.00		
	OsteoMatrix	4 capsules	1000	400.00		
	Vita-Lea Gold Vitamin K Formula high Potency Multivitamin & Mineral	2 tablets	450	400.00		
	Chewable Cal Mag Plus	4 chewtabs	1000	200.00		
	Cinch 3-in-1 Inch Loss Plan Boost	3 tablets	300	260.00		
Sciele Pharma	OptiNate	1 tablet	200	400.00		RX only
Solaray	Iron Free Spectro Multi-Vita-Min	6	500	400.00		

		capsules				
	Mens Golden Multi-Vita-Min	3 capsules	75	400.00		
	Multi-Vita Mega-Mineral Multi-Vita-Min	4 capsules	420	400.00		
	Once Daily High Energy Multi-Vita-Min	1 capsule	10	400.00		
	Once Daily Softgel with Lutein Multi-Vita-Min	1 softgel	25	400.00		
	Provide Multi-Vita-Min	2 softgels	200	400.00		
	Spectro 50 Plus Multi-Vita-Min	4 capsules	200	800.00		
	Spectro Energy Multi-Vita-Min	4 capsules	250	800.00		
	Spectro Kid Multi-Vitamin	2 tablets	200	400.00		
	Spectro Man Multi-Vita-Min	4 capsules	200	400.00		
	Spectro Woman Multi-Vita-Min	4 capsules	400	800.00		
	Twice Daily Multi-Vita-Min	2 capsules	200	400.00		
	Vegetarian Spectro Multi-Vita-Min	6 capsules	500	400.00		
	VitaPrime for Men Multi-Vita_min	4 capsules	400	400.00		
	VitaPrime for Women Multivitamin and Multimneral	4 capsules	400	400.00		
	Womens Golden Multi-Vita-min	3 capsules	75	400.00		
	YumAid Multi-Vita-Min Punch	1tsp	50	400.00		
Solgar	Adv Proanthocyanidin Complex	2 capsules	170	800.00		
	Calcium Magnesium with Vitamin D	5 tablets	1000	400.00		
	Earth Source Multi-Nutrient	3 tablets	250	400.00		
	Female Multiple	3 tablets	400	400.00		
	Formula V VM-75 Multivitamin with Chelated Minerals	2 capsules	20	400.00		
	Formula VM-2000	2 tablets	50	400.00		
	Formula VM-Prime for Adults 50 Plus Iron Free	1 tablet	20	400.00		
	Iron Free Formula VM-75	1 tablet	20	400.00		
	Kangavites Complete Childrens Formula	2 tablets	128	200.00		
	Male Multiple	3 tablets	400	400.00		
	Omnium Multiple Vintamin and Mineral Formula Iron Free	2 tabletws	25	200.00		
	Prenatal Nutrients	4 tablets	1300	400.00		
Source Naturals	Advanced One Multiple (witn and without Iron)	1 tablet	50	400.00		
	Advanced Triple Boron with Calcium 1000mg	2 capsules	500	400.00		
	Calcium & Magnesium 300mg	1 tablet	200	500.00		

	Calcium Hydroxyapatite	2 tablets	600	500.00		
	Calcium Night 150mg	2 tablets	300	100.00		
	Calcium 200mg	1 tablet	200	500.00		
	Elan Vital Multiple	6 tablets	200	400.00		
	Life Defense	4 tablets	95	200.00		
	Life Force	4 capsules	100	1000.00		
	Mega Kid	1 wafer	20	200.00		
	Mens Life Force	3 tablets	100	400.00		
	Mothers Choice	4 tablets	615	400.00		
	Spirulina	2 tablets	106	400.00		
	Ultra	6 tablets	125	400.00		
	Womens Life Force	3 tablets	200	400.00		
Sundown	Advanced SunVite	1 tablet	162	400.00		
	Calcium 600 + D	1 capsule	600	200.00		
	Calcium Oyster Shell 1000mg	3 tablets	1000	400.00		
	Complete Daily with Lutein	1 caplet	162	400.00		
	Daily Multi & Min	1 caplet	162	400.00		
	Daily Multiple 50+ Iron Free with Lutein & Lycopene	1 caplet	200	400.00		
	Multiple Complete Womens	1 caplet	250	400.00		
	Naturals Prenatal Formula	1 tablet	200	400.00		
	One Daily Multiple for Women	1 caplet	400	400.00		
	Prenatal Vitamin and Mineral Formula	1 tablet	200	400.00		
	Vitamins to Go Womens	1 packet	660	125.00		
Super Nutrition	Calcium Blend	3 tablets	1000	1000.00		
	Longevity	1 tablet	68	400.00		
	Menopause Multiple Blend	8 tablets	750	500.00		
	Mens Blend	3 tablets	300	500.00		
	Simply One Prenatal	1 tablet	210	500.00		
	Simply One - One Per Day	1 tablet	33	400.00		
	Simply Perfect Kids	4 tablets	120	400.00		
	Super Blend	4 tablets	500	500.00		
Ther-RX	PrimaCare Softgel	1 softgel	400	400.00		RX only
	PrimaCare Advantage	1 softgel	250	230.00		RX only
	PrimaCare ONE	1 capsules	150	170.00		RX only
Thompson	Adult Plex	3 tablets	300	400.00		
	All in One Multivitamin Iron Free	1 capsule	100	400.00		
	Coachs Formula with Enzymes	2 tablets	333	133.00		
	Mega 80	1 tablet	45	600.00		
	Multi Formula for Women	2 capsules	300	200.00		
	Multi Vitamins with Minerals	2 tablets	170	200.00		
	Nuplex with Iron	1 tablet	120	400.00		

	Prenatal Formula	2 tablets	68	610.00		
	Teenplex Multivitamin	2 tablets	200	400.00		
TwinLab	Daily One Caps (with or without Iron)	1 capsule	25	400.00		
	[name] (various flavors)	1 tablet	100	400.00		
	[name] Bone Formula	1 tablet	500	200.00		
	[name] formula	2 capsules	500	400.00		
	Dualtabs Mega Vitamin and Mineral formula	2 tablets	500	200.00		
	Allergy Multi Caps	2 capsules	333	133.00		
	Animal Friends Kids Chewable (various flavors)	1 chewable	100	400.00		
	Bone Support with Ostivone	4 tablets	1500	800.00		
	Cal Quick Liquid	5ml	500	100.00		
	Calcium 500 with Magnesium & Vitamin D	1 tablet	500	200.00		
	Calcium Citrate Chewable	4 wafers	1000	400.00		
	Pre-Natal Care	2 capsules	400	400.00		
	Womens Ultra Daily	4 capsules	510	400.00		
Usana	Active Calcium	4 tablets	800	400.00		
	Body Rox Active Calcium Chewable	4 chewtabs	800	400.00		
	Essentials Usanimals	1 tablet	75	100.00		
	HealthPak	1 packet	335	1000.00		
VegLife	MultiVeg Energy	4 tablets	34	400.00		
	MultiVeg Energy with Lutein and Iron	3 capsules	50	800.00		
	SpectroVeg High Energy	6 tablets	500	400.00		
	Vegan Cal-Mag Citrate Plus Vitamin D	3 tablets	500	200.00		
	Vegan Kids	2 tablets	30	400.00		
	Vegan One Multi with Iron	1 tablet	50	400.00		
	Vital Teen Boys	2 capsules	150	800.00		
	Vital Teen Girls	2 capsules	150	1000.00		
Vitabase	Active Mans Formula	1 tablet	50	400.00		
	Childrens Multiple Liquid	30ml	200	220.00		
	Coral Calcium 1000mg	1 capsule	250	200.00		
	Hair, Skin & Nails Liquid	3 liquicaps	300	200.00		
	Kids Chewable Calcium	2 chewtabs	200	200.00		
	PreNatal Plus	4 tablets	800	400.00		
	Super Calcium & Magnesium	3 tablets	1000	200.00		
	Super Softgel Formula	2 softgels	200	400.00		

Vitaline	Total Formula	1 tablet	100	400.00		
	Total Formula 2	1 tablet	100	400.00		
	Maximum Red	1 tablet	83	67.00		
Vitamin Shoppe	1 Daily	1 tablet	100	400.00		
	Ultimate Man	2 tablets	200	1000.00		
	Ultimate Woman	2 tablets	500	1000.00		
	Calcium Citrate	2 tablets	333	204.00		
Vitamin World	Bone Reinforcer with Hydroxyapatite	4 tablets	1200	400.00		
	Calcium Magnesium with D	3 tablets	1000	400.00		
	Coral Calcium 500mg Plus Vitamin D	2 capsules	370	400.00		
	Daily 3 Multiple with Cholesterol Regulators	3 capsules	106	800.00		
	Green Source	3 tablets	250	400.00		
	Spirulina Soy protein Drink	1 scoop	300	400.00		
	Thervim M	1 tablet	40	400.00		
	Ultra Vita Man timed release	2 tablets	200	200.00		
Whole Health	Cal-Mag Calcium & Magnesium Citrates 1400mg	4 tablets	1000	400.00		
	Childrens Chewable Multivitamin	2 chewtabs	55	400.00		
	GreenHealth Natural Multi	2 capsules	50	100.00		
	HerHealth	4 capsules	780	600.00		
	HisHealth	3 capsules	272	400.00		
	Prenatal Health	4 tablets	1000	220.00		
	Super Multi Plus	3 tablets	400	400.00		
Whole Source	Mature Adults Multi Mineral with Herbs	1 tablet	165	400.00		
Windmill	Ezcal 2000 + D (regular tablets & chewables)	1 tablet	1000	400.00		
Women's Health America	ProCycle Gold	1 tablet		100.00		
Wonder Labs	Multivitamin/Multimineral with Beta Carotene & Lycopene	1 tablet	162	400.00		
	Pure coral Calcium 2500mg	3 capsules	2500	200.00		
Xanodyne	Duet DHA	1 tablet	200	400.00		RX

						only
	Duet Chewable	1 tablet	100	400.00		RX only

Appendix VI: Dietary calcium and vitamin D intake calculator

Questionnaire adapted from Rapid
Vit D data from USDA database from NDS

INSTRUCTIONS

Use the excel spreadsheet to calculate the average daily dietary intake of calcium and vitamin D from food.
Please ask the participant to recall food items eaten over the last 3 days.

Ask the participant about each food item in column "B" and record how many servings (size of each serving detailed in spreadsheet) he/she ate over the last 3 days. Enter the number of servings in column "C". The total amount of calcium and vitamin D from that food item will be automatically calculated in the spreadsheet and displayed in row 65: these are the numbers to input into the spreadsheet.

The total DAILY intake of calcium and vitamin D (an average of the 3 day intake) will be automatically calculated and displayed in row 65: these are the numbers to input into the spreadsheet using the File Exchange Utility located on the FSTRF website (www.fstrf.org)

Food	servings	Calcium/serving (l VitD/serving (mcg)	CA Total (mg)	D Total (IU)
Milkyogurt/cheese				
cheese (1 oz or 6 tbsp)	200	0.09	0	0
cottage cheese (1/2cup)	50	0.03	0	0
custard, pudding, cream pie (1/2 cup)	150	1.43	0	0
ice cream, frozen yogurt, milkshake (1 cup)	200	1.26	0	0
yogurt (1 cup)	388	0.03	0	0
butter (1 tbsp)	100	0.20	0	0
milk (1 cup)	300	2.50	0	0
latte or mocha latte (1 cup)	220	2.00	0	0
café au lait (1 cup)	99	2.00	0	0
cappuccino (1 cup)	250	2.00	0	0
Fortified orange juice (1 cup)	350	2.50	0	0
soy milk, unfortified (1 cup)	10	0.00	0	0
soy milk, fortified (1 cup)	300	2.50	0	0
cream soup/sauce (1 cup)	200	0.18	0	0
macaroni and cheese (1 cup)	250	0.23	0	0
pizza (1 slice)	250	0.03	0	0
quiche (1 slice)	250	1.01	0	0
Fruits/Vegetable				
broccoli or cooked greens (1/2 cup)	100	0.00	0	0
other vegetables (1/2 cup)	30	0.00	0	0
fruit (1/2 cup or 1 small)	30	0.00	0	0
Bread/Cereal/Rice/Pasta				
bread (1 slice)	20	0.00	0	0
calcium enriched bread (1 slice)	102	0.00	0	0
cereal (1 oz)	20	0.94	0	0

smoked eel (1oz)				0.89					
herring (1oz)				11.54					
canned salmon with bones (3oz)	150			9.91					
canned sardines with bones (3oz)	400			3.91					
shrimp (3oz)	100			3.04					
oysters (7-9)	100			9.36					
tofu (2.5x2.5x1 inch)	100			0.00					
peanuts (1/2 cup)	30			0.00					
egg (1)	30			0.56					
Fat/Sugar/Alcohol									
cake (1 slice)	40			0.12					
beer (12 oz)	10			0.00					
cola (12 oz)	10			0.00					
chocolate (1 oz)	50			0.00					
TOTAL INTAKE PER DAY									0

BIostatISTICS
RESEARCH CENTER

CCTG 595

**A Multicenter, Randomized Study of Text Messaging to Improve
Adherence to PrEP in Risky MSM**

Statistical Analysis Plan

March 18, 2016

Investigators: [name] & [name]

Statistician: [name], MS

CCTG Biostatistics Core Director: [name]

Contents

1 Introduction	3
2 Study Design	3
3 Study Objectives	4
3.1 Primary Objective	4
3.2 Secondary Objectives	4
4 Subject Disposition	5
4.1 Participant Flow Summary	5
4.2 Evaluation of Premature Discontinuation from Study	5
5 Evaluation of Demographics and Baseline Characteristics	6
6 Evaluation of Primary Objective	7
7 Evaluation of Secondary Objectives	9
7.1 Secondary Objective 1	9
7.2 Secondary Objective 2	9
7.3 Secondary Objective 3	9
7.4 Secondary Objective 4	9
8 Evaluation of Safety Measures	10
9 Software	11

1 Introduction

This document describes the statistical analysis plan (SAP) for the CCTG595 clinical trial.

2 Study Design

CCTG595 is a controlled, open-label, two-arm, randomized (1:1) clinical demonstration project to determine if the use of a text message based adherence intervention (iTAB) improves retention and adherence to PrEP compared to standard of care (SoC) PrEP delivery.

The study is expected to enroll a total of 400 subjects. Eligible subjects will include HIV-uninfected men who have sex with men (MSM) and male to female (M to F) transgender individuals who have sex with men at least 17 years of age and who have a recent history of high risk transmission behavior. All subjects will start PrEP with TDF+FTC fixed dose combination given once daily. Subjects will be randomized 1:1 to either the iTAB text messaging adherence reminder intervention with SoC or the SoC alone arm. The randomization will be stratified by clinic site. Subjects placed into the iTAB intervention arm will receive a personalized, automated texting system to maintain adherence and retention. Both groups will receive access to PrEP in accordance with standardized comprehensive methods of prescribing, risk reduction counseling, adherence counseling, and clinical assessments that include safety monitoring, as well as HIV and STD screening. The study will continue for 48 weeks after randomization of the last participant (up to about 2.5 years).

3 Study Objectives

3.1 Primary Objective

To compare adherence to fixed dose TDF/FTC between subjects randomized to receive SoC plus text message reminders versus SoC, when used for pre-exposure prophylaxis among MSM at high risk for HIV acquisition.

Hypothesis

MSM and transgender M to F having sex with men with high risk of HIV acquisition randomized to the iTAB intervention will have higher adherence to TDF/FTC for PrEP over 48 weeks compared to MSM that have comprehensive SoC alone.

3.2 Secondary Objectives

1. To determine factors associated with poor adherence/lost to PrEP in study participants. Factors will include demographics, ongoing substance use, untreated mental illness, socioeconomic status, low health/HIV and system literacy, fear of disclosure and non-English language.
2. To determine the rate of HIV seroconversion in PrEP users and compare the iTAB to SoC arms for number of new infections as a proportion at 48 weeks and end of the study.
3. To measure acquisition of other sexually transmitted infections (STIs); the proportion of subjects with any new STI at any site will be compared between the iTAB to SoC arms at 48 weeks and end of the study.
4. To evaluate changes in risk behavior after initiation of PrEP (risk compensation) comparing baseline to subsequent visits for number of HIV positive/unknown status partners and any unprotected anal intercourse with an HIV positive/unknown status partner.
5. To evaluate the safety and tolerability of daily TDF/FTC given for PrEP including discontinuation for any adverse event, serious adverse events, and adverse events (grade 2 or higher).

4 Subject Disposition

4.1 Participant Flow Summary

Tables will summarize the following, by site, by study arm, and overall.

- The number of subjects screened
- The number of subjects screening failed
- The number of subjects randomized
- The number of subjects completed week 48 visit
- The number of subjects completed study
- The number of subjects prematurely discontinued study

Reasons for screening failure and premature discontinuation will be summarized by frequency and category for reason. Listings will also be provided.

4.2 Evaluation of Premature Discontinuation from Study

Proportions of subjects prematurely discontinued the study will be compared between the study arms using Fisher's exact test. The numerator will be the number of subjects who marked other than 'complete the study' as the primary reason in the Termination form. The denominator will be the number of subjects who were randomized.

Time to premature discontinuation will be summarized overall, and by study arm using the method of Kaplan and Meier. The cumulative probability of premature discontinuation will be estimated overall and by arm, with 95% confidence interval. Log-rank test will compare time to premature discontinuation between randomized arms.

The survival indicator will be defined (1=early discontinued the study; 0=completed the study). The event time and censoring time will be defined from the baseline date to the termination date indicated in the Termination form.

5 Evaluation of Demographics and Baseline Characteristics

Tables will summarize the study population at baseline, overall and by study arm. Descriptive statistics will be presented as N, mean, standard deviation, minimum, 25th Q, median, 75th Q, maximum for continuous variables; frequency tables (row, column percentages) will be used for categorical variables. Statistical comparisons will be performed between randomized arms using Wilcoxon Rank Sum Test (for continuous variables) or Fisher's exact test (for categorical variables). The following variables will be examined at baseline:

- Age
- Race/Ethnicity (White, Black, Hispanic, Other)
- Education
- Household average monthly income
- Inclusion criteria
- STI status
- Language (English vs Other)
- Substance use (SCID screen)
 - Any drug use reported other than alcohol and marijuana
 - Meth use
- AUDIT score
- DAST score
- Sexual Compulsivity Score (SCS)
- HIV literacy score

6 Evaluation of Primary Objective

The primary objective of the study is to compare the adherence to PrEP during the 48-week study period between the iTAB intervention group and the SoC group.

The primary analysis will be conducted on the modified intent-to-treat (mITT) population (i.e. randomized subjects who started PrEP).

Primary Adherence Endpoint

The primary adherence endpoint will be a binary endpoint (Yes/No) based on DBS samples from two visits (week 12 visit and the last on-drug visit over the 48 weeks). Both visits should have a detectable TFV-DP level >719 fmol/punch (consistent with taking four or more doses per week) to be considered adherent. If the last on-drug visit was at week 12 (i.e. the subject had only one DBS sample), adherence will only be determined by that sample. If a subject discontinued study before week 12 (i.e. had no DBS samples at all), the subject will be considered non-adherent.

Additional Secondary Adherence Endpoints

- Self-reported Adherence: a binary composite endpoint of continued on PrEP and $\geq 90\%$ self-reported adherence to TDF/FTC over 48 weeks. The endpoint will be defined yes if 14 or 15 out of 15 days were reported 'adherent' on the 3-day recall on the clinical assessment form collected at w4, w12, w24, w36, and w48. Note if a subject discontinued the study or missed any visits before w48, those visits will be considered not adherent in the calculation.
- a continuous version of the self-reported adherence measure: defined as percent days that were reported adherent based on the clinical assessment form. In the case where the adherence measure is missing (either due to the subject discontinued PrEP, or missed visit, or other reasons), two approaches will be applied.
 - treat the missing as 'not adherent'. This assumes the worst case (i.e. assume all the missing is related to adherence).
 - ignore the missing. This assumes the best case (i.e. assume all the missing is not related to adherence).
- FTC Adherence: a binary endpoint of having four of four detectable qualitative FTC plasma concentrations (measured at w12, w24, w36, and w48) over 48 weeks. Detectable FTC is defined as a quantitative level of ≥ 0.35 ug/ml consistent with taking a dose in past 24 hours. Note missing will be treated as not detectable.
- Similar outcome as the primary endpoint where we will use the cut-off of ≥ 1246 fmol/punch consistent with taking seven doses per week.
- Proportion of subjects on PrEP at week 48.

Descriptive Analysis

Descriptive analysis will look at self-reported adherence, FTC adherence and TFV-DP adherence measures by visit. Continuous outcome will be summarized with N, min, Q1, median, Q3, and max, by study arm and overall. Binary endpoint will be summarized with frequency tables, by study arm and overall. Wilcoxon rank sum test will be used for comparison for continuous outcome; Fisher's exact test will be used for binary outcome.

Statistical Inference

A logistic regression model will be performed to compare the adherence over 48 weeks between the two groups. The model will include baseline factors (refer to the baseline variable list) as covariates if they are found unbalanced between the study arms (with $p < 0.1$) and also univariately associated with the outcome ($p < 0.15$). Interactions between each of the covariates and study arm will also be assessed individually. Significant interactions ($p < 0.05$) will be included in the final model.

7 Evaluation of Secondary Objectives

7.1 Secondary Objective 1

To determine factors associated with poor adherence/lost to PrEP in study participants. Factors will include demographics, ongoing substance use, untreated mental illness, socioeconomic status, low health/HIV and system literacy, fear of disclosure and non-English language.

This objective will be assessed along with the primary objective analysis. The final primary multivariable model will be able to answer this question.

7.2 Secondary Objective 2

To determine the rate of HIV seroconversion in PrEP users and compare the iTAB to SoC arms for number of new infections as a proportion at 48 weeks and end of the study.

Number and proportion of subjects with HIV-seroconversion at 48 weeks will be summarized by study arm and overall. Fisher's exact test will be used for comparison. Same analysis will also look at the rate of seroconversion during the whole study period.

7.3 Secondary Objective 3

To measure acquisition of other sexually transmitted infections (STIs); the proportion of subjects with any new STI at any site will be compared between the iTAB to SoC arms at 48 weeks and end of the study.

Any new STI will be defined as positive results from Gonorrhea (GC) or Chlamydia (CT) at any site or positive syphilis RPR result with titer $>1:4$ based on the STI form collected after baseline visit.

Sensitivity analysis will also be performed looking at STI by testing as well as self-reported STI (outside diagnosis) based on the clinical assessment form.

7.4 Secondary Objective 4

To evaluate changes in risk behavior after initiation of PrEP (risk compensation) comparing baseline to subsequent visits for number of HIV positive/unknown status partners and any unprotected anal intercourse with an HIV positive/unknown status partner.

Descriptive summaries will be provided by visit (at w4, w12, w24, w36, and w48). Wilcoxon signed rank test will be used to compare the number of HIV positive/unknown status partners at each follow-up visit to the baseline visit. GEE model will be used to assess the change in risk behavior over time.

8 Evaluation of Safety Measures

Safety data will be reported for all the randomized subjects. Tables will summarize the number of serious adverse events, adverse events (grade 2 or higher), PrEP discontinuation due to adverse events, by study arms and overall. Fisher's exact test will be used to compare the rates between the two groups. The time to TDF/FTC discontinuation due to adverse events will be compared between groups using the log-rank test and plotted using Kaplan-Meier curves.

9 Software

Statistical software R (version 3.1.1) will be used <http://www.r-project.org>.

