Clinical Trials Specialist

[name]
Staff Research Associate
University of California, San Diego
Antiviral Research Center
[name]
San Diego, CA 92103
[contact]
[contact]
E-mail [contact]

Statistician

[name]
Associate Professor, Division of Biostatistics and Bioinformatics
Director, CCTG Biostatistics Core
Co-Director, Biostatistics Research Center (BRC)
University of California, San Diego
[name]
La Jolla, CA 92093-0717
[contact]
E-mail [contact]

Study Monitor and Data Unit

[name]
Medical Monitor, Study Coordinator, CCTG Data Unit
University of California, San Diego
Antiviral Research Center
[name]
San Diego, CA 92103
[contact]
[contact]
E-mail [contact]

Lab Technician

[name]
Phlebotomist and Lab Manager
University of California, San Diego
Antiviral Research Center

[name]
San Diego, CA 92103
[contact]
[contact]
E-mail [contact]

LIST OF ABBREVIATIONS

AE	Adverse Event
ALERT	Active Linkage, Engagement, and Retention to Treatment
ARV	Antiretroviral Therapy
CCTG	California Collaborative Treatment Group
CD4	CD4 Lymphocytes
CRF	Case Report Form
CT	Chlamydia
DSMB	Data Safety and Monitoring Board
GC	Gonorrhea
HAART	Highly Active Antiretroviral Therapy
HIV-1	Human Immunodeficiency Virus – 1
iTAB	Individualized Texting for Adherence Building
mITT	Modified Intention to Treat
MSM	Men who have Sex with Men
NAAT	Nucleic Acid Amplification Test
PLWH	Persons Living With HIV/AIDS
PrEP	Pre-Exposure Prophylaxis
RPR	Rapid Plasmin Reagin
SAP	Statistical Analysis Plan
SAE	Serious Adverse Event
SoC	Standard of Care
STI	Sexually Transmitted Infection
TPPA	Treponema Pallidum Particle Agglutination Assay
VAS	Visual Analog Scale
VDRL	Venereal Disease Research Laboratory

[figure not shown]
SCHEMA

Design: CCTG 595 is a controlled, open-label, two-arm, randomized (1:1) clinical demonstration project to determine if the use of a text-message based adherence intervention (iTAB) improves retention and adherence to PrEP compared to standard of care (SoC) PrEP delivery.

Duration: Each subject will be followed for up to 48 weeks after enrollment of the last subject to a maximum of 96 weeks. The primary endpoint will be measured at 48 weeks.

Sample Size: A total of 400 subjects will be randomized, 200 per arm.

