8.0 CRITERIA FOR TREATMENT DISCONTINUATION

8.1 Criteria for Discontinuation from Study

- 8.1.1 Diagnosis of HIV infection.
- 8.1.2 Request by the subject to withdraw.
- 8.1.3 Request of the primary care provider if s/he thinks the study is no longer in the best interest of the subject.
- 8.1.4 Clinical reasons believed life threatening by the study physician, even if not addressed in the toxicity management of the protocol, and can no longer continue in follow up.
- 8.1.5 Subject judged by the investigator to be at significant risk of failing to

comply with the provisions of the protocol as to cause harm to self or seriously interfere with the validity of the study results.

- 8.1.6 At the discretion of the CCTG, FDA, CHRP or pharmaceutical sponsors.
- 8.1.7 Misses two consecutive scheduled visits prior to 48 weeks.
- 8.1.8 Misses one scheduled visit after 48 weeks.

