9.6.2 Analysis of Primary Outcome

The primary analysis will use a two-sample binomial test for proportions to determine if the intervention arm will produce an improved composite endpoint rate compared to the standard of care arm. Fisher's exact test will be used along with a 95% confidence interval. As a sensitivity analysis, the two components of the composite primary endpoint will be analyzed separately (retained on PrEP and Adherence > 90%). A Fisher's exact test will be used to compare rates of study discontinuation between the active intervention arm versus standard of care arm.

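### SAP 4.2 pools terminations across a missed-visit rule that changes at week 48, so whole-study discontinuation cannot be read as drop-out alone

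*SAP*

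**What the plan says.** SAP 4.2 plans the between-arm comparison: "Proportions of subjects prematurely discontinued the study will be compared between the study arms using Fisher's exact test". The event covers every reason except completion: "The numerator will be the number of subjects who marked other than 'complete the study' as the primary reason in the Termination form". The denominator is everyone randomised. The same event feeds a Kaplan-Meier estimate by arm and a log-rank test, on this time scale: "The event time and censoring time will be defined from the baseline date to the termination date indicated in the Termination form". There is no cut at week 48 and no split by reason.

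Protocol 9.6.2, the section on the primary outcome, also plans the comparison and names no time point: "A Fisher's exact test will be used to compare rates of study discontinuation between the active intervention arm versus standard of care arm". Under Protocol 9.0 the SAP takes precedence where the two differ.

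Protocol 8.1 lists what ends participation. Two items concern missed visits:

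- 8.1.7: "Misses two consecutive scheduled visits prior to 48 weeks"
- 8.1.8: "Misses one scheduled visit after 48 weeks"

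The Protocol Schema sets follow-up: "Each subject will be followed for up to 48 weeks after enrollment of the last subject to a maximum of 96 weeks". It puts the primary endpoint at week 48 and names retention as part of the trial's question. SAP 2 gives a duration of up to about 2.5 years, which can be read as the calendar length of the study rather than one participant's follow-up.

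Three other parts of the SAP bear on this. SAP 4.1 counts week-48 completers by arm and tabulates reasons for early discontinuation. SAP 6 lists the share still taking PrEP at week 48 as a secondary adherence endpoint. SAP 3.2 asks for HIV and STI outcomes both at 48 weeks and at study end, a separation that SAP 4.2 does not make for retention.

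**The concern.** The same behaviour is classified differently on either side of week 48. A participant who misses only the week 24 visit does not meet a termination criterion. One who misses only week 60 does, and becomes an event in SAP 4.2. Exposure to the later rule also depends on enrolment date, because the last participants enrolled have little or no follow-up after week 48.

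Two things are at stake. The first is interpretation: a steeper fall in the curve after week 48, or a high whole-study rate, could be taken as loss of engagement when part of it is removal for one missed visit. The Fisher proportion also refers to no fixed time point, since follow-up varies between participants. The second is sensitivity: if the later rule removes similar fractions of both arms, a real difference in retention over the 48 weeks of interest is diluted in the pooled Fisher and log-rank comparisons.

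**Working it through.** **The plan's own figures.** Protocol 9.4 gives power of 94% (30% vs 15%) and 84% (30% vs 17%) with 200 per arm and two-sided alpha 0.05. Full enumeration of Fisher's exact test gives 94.0% and 84.5%, so both reproduce. They concern the composite endpoint. No power, missed-visit rate or drop-out rate is stated for retention.

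**Inputs.** Visits fall at weeks 4, 12, 24, 36 and 48 (five), then at 60, 72, 84 and 96 (none to four, by enrolment date) (Protocol 3.1 and 6.1). Protocol 3.3 plans 3467 samples for 400 participants: 3467/400 = 8.67 visits each, or 8.67 − 5 = 3.67 after week 48. The miss probability *m* per visit and true drop-out *d* per visit interval are assumptions.

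**Step 1: the rules alone, with independent misses and no other cause of termination.** The week 48 visit is counted under the earlier rule.

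Earlier rule, five visits: P = 1 − [(1−m)^5 + 5m(1−m)^4 + 6m²(1−m)^3 + m³(1−m)^2].
At m = 5%: 1 − (0.77378 + 0.20363 + 0.01286 + 0.00011) = 0.0096.

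Later rule, k visits: P = 1 − (1−m)^k.
At m = 5%: k = 4 gives 1 − 0.8145 = 0.1855; k = 2 gives 1 − 0.9025 = 0.0975.

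| m | Earlier rule, 5 visits | Later rule, 2 visits | Later rule, 4 visits | Two-consecutive rule over all 9 visits |
|---|---|---|---|---|
| 2% | 0.2% | 4.0% | 7.8% | 0.3% |
| 5% | 1.0% | 9.8% | 18.5% | 1.9% |
| 10% | 3.7% | 19.0% | 34.4% | 7.2% |

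If the week 48 visit is left out of the earlier rule (four visits), it removes 0.7% at m = 5% and 2.8% at m = 10%.

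**Step 2: add true drop-out.** Simulation with 300,000 participants per setting. The entries are the share of all discontinuations due only to the later rule, as *m* runs over 2-15%.

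| d per interval | Mean 3.67 visits after week 48 | Uniform 0-4 visits after week 48 |
|---|---|---|
| 0 | 84-98% | 75-96% |
| 1% | 44-72% | 35-62% |
| 2% | 28-62% | 20-51% |
| 3% | 20-54% | 14-44% |
| 5% | 12-42% | 8-33% |

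**Step 3: possible dilution (illustrative).** Take true drop-out of 20% vs 10% with 200 per arm. If the later rule also removes a fraction r of those remaining in each arm, the observed proportions are p + r(1 − p). Power is by normal approximation, two-sided 0.05, without continuity correction; Fisher's test would give somewhat less.

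| r | Observed proportions | Power |
|---|---|---|
| 0 | 20% vs 10% | 80% |
| 10% | 28% vs 19% | 57% |
| 20% | 36% vs 28% | 40% |
| 30% | 44% vs 37% | 30% |

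**The case against.** SAP 4.2 sits under subject disposition. Someone removed under 8.1.8 did leave early, so the count is correct for that purpose. The rules are identical in both randomised arms. The week-48 estimate can be read from the planned curve, and SAP 4.1 already reports week-48 completers and reasons. SAP 6 adds the proportion on PrEP at week 48. Step 1 assumes independent misses; clustered misses would raise the earlier rule's share. It also ignores the interim visit allowed in Protocol 6.1, and the documents do not say whether that visit cancels a miss.

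Much of this stands. A reader might infer that the whole-study rate and curve mostly measure the later rule. The documents do not support that: Step 1 sets other drop-out to zero, Protocol 8.1 lists six other reasons for leaving, and once drop-out is allowed the share spans 8% to 98% and stays below half at d = 5%. A reader might also infer that the tests are biased. With the same rules in both arms, they are not under no effect.

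What the objection does not remove is the gap in the formal comparison. The SAP 4.1 tables are descriptive. Being on PrEP at week 48 is not study retention, because Protocol 6.4 lets participants stop drug and stay on study. The only planned tests of study retention use the pooled event.

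**Conclusion.** The point holds as one of interpretation and possible dilution. The event definition changes at week 48 inside a single comparison, and SAP 4.2 does not acknowledge it. The whole-study discontinuation rate, the curve after week 48 and the log-rank test cannot be read as drop-out alone. The curve up to week 48 is unaffected.

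Visit for visit, the contrast between the rules is large: about 1.0% against 18.5% at an assumed 5% independent miss rate over five and four visits. Its weight among all terminations cannot be fixed from the documents. The later rule passes half mainly when true drop-out is about 1-2% per interval or less and misses are at least 5-10% per visit. Dilution assumes that the rule removes similar fractions in both arms. If text messaging itself affects attendance after week 48, the pooled difference could move either way.

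This is not the primary endpoint, but it is a planned between-arm test on a stated aim of the trial, so the change is worth making.

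**What to change.** In SAP 4.2, make the main retention comparison run through week 48. Apply Fisher's exact test to the proportion terminated by week 48, and censor the Kaplan-Meier curve and log-rank test at week 48. Keep the whole-study analysis as supplementary, with a sentence saying that the missed-visit rule changes at week 48. Report later terminations separately by arm, with removals for a single missed visit as their own category where the Termination form allows. The form is not in the documents, so this needs checking.

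State the cut-off so that it works for people with no week 48 visit. Say how a termination triggered by missing week 48 is assigned, since 8.1.7 and 8.1.8 refer to before and after 48 weeks and leave that visit unplaced. Say also whether an interim visit counts as attendance.

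The cost is SAP wording. The termination date and primary reason are already collected, and the site rule is unchanged. The small downside is that discontinuation after week 48 becomes supplementary or descriptive.
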